2.8.1.1 Adverse events of special interest / grouping of AEs

N/A

2.8.2 Deaths

AEs that lead to death are outlined in [Section 2.8.1](#).

2.8.3 Laboratory data

The summary of the data for laboratory evaluations will be presented for both types of laboratory tests (hematology and biochemistry).

Descriptive summary statistics for the absolute values and changes from Baseline at each study visit will be presented. Descriptive summaries will be presented by type and by laboratory test.

For each parameter, shift tables will be produced in order to compare patient Baseline laboratory evaluation with the observed value at each visit. For these shift tables, the normal laboratory ranges will be used to evaluate whether a particular laboratory test value is normal, low, or high at each visit relative to whether or not the Baseline value was normal, low, or high. These summaries will be presented by laboratory test.

The expanded laboratory ranges and the clinically notable abnormalities of key laboratory tests are given in Appendix 9, Section 13.9 of the study protocol version 5.

2.8.4 Other safety data

2.8.4.1 ECG and cardiac imaging data

N/A in this section (see [Section 2.3.3](#)).

ECG collected at screening will be summarized as part of Baseline characteristics (see [Section 2.3.3](#))

2.8.4.2 Vital signs

Vital signs will be presented for the whole study period. Analysis of the vital sign measurements using summary statistics for the absolute values and changes from Baseline at each non-missing post-Baseline visit will be performed. These descriptive summaries will be presented by vital sign parameter.

The number and the percentage of subjects with notable vital signs will be presented. The criteria for notable vital sign abnormalities are provided in Appendix 8, Section 13.8 of the study protocol version 5.

All information collected will be listed by patient and visit. Notable abnormal values will be flagged.

2.9 Pharmacokinetic endpoints

N/A

2.10 PD and PK/PD analyses

N/A

2.11 Biomarkers

N/A

2.12 Other exploratory analyses

Exploratory analyses in this subsection will be on the FAS (observed data only).

Correlations between scores

Correlations between saSPI (s, p, i) and DLQI, proSPI (s, p) and saSPI (s, p), saSPI (s) and PASI, proSPI (s) and saPASI, saSPI (s) and saPASI will be evaluated using the Spearman correlation coefficient. Scatterplots will be presented at Week 16.

Responsiveness to change

An analysis of the SPI responsiveness to change will be led in order to investigate if reductions in psoriasis severity based on PASI scores would be accompanied by corresponding reductions in proSPI (s) and saSPI (s) scores at Week 16. This analysis will be performed by the calculation of receiver operating characteristic (ROC) and area under the curve (AUC). Three criteria of response will be examined to evaluate each score: $\geq 50\%$, $\geq 75\%$, $\geq 90\%$, and 100% reduction in PASI score.

For each binary PASI response (e.g. for PASI75, 1 if $\geq 75\%$ and 0 otherwise), a logistic regression will be performed where proSPI (s) and saSPI (s) are the independent variables in separate models. The nonparametric methods described in DeLong et al. (1988) will be used to compute the AUC value and 95% CIs for each curve. From the regression models, odds ratios along with their 95% CIs, and AUC values along with their 95% CIs will be presented.

Sexual dysfunction

To explore sexual dysfunction in the subset of patients willing to complete sexual function questionnaire, descriptive summary statistics will be presented for absolute values and change from Baseline for BISF-m and BISF-w scores at all assessment periods.

Each of the BISF-m and BISF-w index contain seven dimensions (thoughts/desire, arousal, frequency of sexual activity, receptivity/initiation, pleasure/orgasim, relationship satisfaction, problems affecting sexual function). Eight scores will be derived from the answers to the

questionnaires: the score of each of the seven dimensions as well as the composite score computed from all dimensions. Details of the calculation are given in [Appendix 5.3](#).

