1.2.3 Exploratory objectives

- to evaluate correlation between saSPI (s, p, i separately) and DLQI.
- to evaluate correlation between proSPI (s, p separately) and saSPI (s, p separately).
- to evaluate correlation between saSPI (s) and PASI.
- to evaluate the ability of SPI to discriminate between responders and non-responders based on PASI response.
- to explore sexual dysfunction using the Brief Index of Sexual Functioning for men/woman (BISF-m or BISF-w) questionnaire in a subset of subjects willing to complete sexual function questionnaire.

2 Statistical methods

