2.5.2 Statistical hypothesis, model, and method of analysis

The following hypothesis will be tested for each co-primary endpoint at the 5% significance level (2-sided):

$$H_0: \mu_d = 0$$

$$H_A: \mu_d \neq 0$$

where μ_d denotes the mean difference of paired observations.

To assess the primary objective, the absolute change from Baseline in proSPI (s) and absolute change from Baseline in saSPI (s) will be analyzed using a paired t-test (Week 16 vs Baseline).

The key assumptions underlying the use of a paired t-test will be checked. In the event the data is non-normal, Wilcoxon signed rank test will be performed.

An adjustment for multiplicity will be performed using the Hochberg procedure and the family-wise type-I-error will be set to $\alpha=5\%$ (2-sided). The adjustment will be applied as follows; if the maximum of the two p-values is rejected at the 5% level (2-sided) then both hypotheses are rejected and statistical significance is claimed for both endpoints. Otherwise if the maximum of the two p-values is not rejected, then the minimum p-value is tested at the 2.5% level (2-sided), if rejected then statistical significance is claimed only for this endpoint.

Descriptive statistics of proSPI (s) and saSPI (s) (Baseline, actual value, absolute and percentage change from Baseline) will be presented by visit for severity score and its components 1A and 1B. The number and percentage of reponses for 1A will be presented by body part. The change from Baseline of proSPI (s) and saSPI (s) will be presented graphically, showing the mean and SE of the change per visit.

The number and percentage of proSPI (s) and saSPI (s) will be presented by visit and by the following score bands: from 0 to 10, > 10 and ≤ 20 , > 20 and ≤ 30 , > 30 and ≤ 40 , > 40 and ≤ 50 . Graph of reponse distribution of proSPI (s) and saSPI (s) will be presented by the aforementioned score bands at Week 16.

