2.13 Interim analysis

No interim analysis is planned in this study.

3 Sample size calculation

The samples size calculation is based on the primary objective of the study which is to evaluate the benefit of secukinumab on the severity and psychosocial burden of psoriasis based on SPI change at Week 16 compared to Baseline in patients suffering from moderate to severe plaque psoriasis.

A similar study by Chularojanamontri et al. (2013) showed that it is possible to detect responsiveness and a minimum clinically important difference (an absolute change of 5 and 7 for proSPI (s) and saSPI (s), respectively) derived from PASI changes with 100 patients. The study showed a SD of 7.35 and 10.35 in change from Baseline at Week 10 in proSPI (s) and saSPI (s) respectively. As the SD at Week 16 is expected to be higher, conservative SD estimates of 14 and 19 will be assumed for change at Week 16 for proSPI (s) and saSPI (s) respectively.

Based on an analysis of paired differences, in order to have at least 90% power to detect a significant clinical difference for each index at the 2.5% level (2-sided), it can be estimated that a sample size of 100 evaluable patients would be sufficient.

Taking into account an anticipated drop-out of 20 patients, 120 patients will need to be included in the study.

4 Change to protocol specified analyses

Any objectives to be assessed until Week 56 will be changed to until end of study.

5 Appendix

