5.4 SAS code

Paired t-test with multiplicity correction

```
/* Perform paired t-test and output p-value on variable DIFF (paired  
difference of two variables of interest). Repeat for other differences */  
proc ttest data=<dataset> sides=2 alpha=0.05 H0=0;  
    var DIFF;
```

```
ods output ttests=ttest_pvalue;
run;

/* Sort all p-values in ascending order */
proc sort data=ttest_pvalue out= allpvaluessorted;
  by probt;
run;

/* Do multiple adjustment on the sorted p-values using Hochberg procedure */
proc multtest pdata(probt)=allpvaluessorted hoc;
run;
```

Receiver Operating Characteristic curve and area under the curve

```
/* The plots=<dataset>(id=probt) specification will display a ROC curve that
will have certain points labeled with their predicted probabilities */
ods graphics on;
  proc logistic data=<dataset> plots=<dataset>(id=probt);
    model <response>(event='1') = <predictor>;
    roc '<predictor's label>' <predictor>;
  run;
ods graphics off;
```

6 Reference

- DeLong, E. R., DeLong, D. M., and Clarke-Pearson, D. L. (1988). “Comparing the Areas under Two or More Correlated Receiver Operating Characteristic Curves: A Nonparametric Approach”. *Biometrics*, 44, 837-845
- Mazer, N. A., Leiblum, S. R., & Rosen, R. C. (2000). “The brief index of sexual functioning for women (BISF-W): a new scoring algorithm and comparison of normative and surgically menopausal populations”. *Menopause*, 7(5), 350-363

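### Does the responsiveness-to-change ROC analysis need its SPI predictor spelled out as a change from Baseline, with a stated form?

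*SAP*

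**What the plan says.** Section 2.12, under the heading on responsiveness to change, sets the aim of finding out whether "reductions in psoriasis severity based on PASI scores would be accompanied by corresponding reductions in proSPI (s) and saSPI (s) scores at Week 16". The tool is an ROC curve with its AUC, for PASI reductions of at least 50%, 75% and 90%, and of 100%. For each binary PASI response, "a logistic regression will be performed where proSPI (s) and saSPI (s) are the independent variables in separate models". Odds ratios and AUCs are reported with 95% confidence intervals, on observed data in the FAS.

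The matching exploratory objective in Section 1.2.3 is "to evaluate the ability of SPI to discriminate between responders and non-responders based on PASI response".

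The template in Section 5.4 reads "model <response>(event='1') = <predictor>", with no variable named.

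Three other places bear on the meaning of change:
- Section 2.1.1.3 defines change from Baseline as the post-Baseline value minus the Baseline value, and defines percentage change separately.
- Section 2.5.2 tests the absolute change in each severity score and summarises each score as "Baseline, actual value, absolute and percentage change from Baseline".
- Section 3 describes the minimum clinically important difference as "an absolute change of 5 and 7 for proSPI (s) and saSPI (s), respectively".

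**The concern.** The aim is about reductions, but the sentence that defines the model gives only the names of the scores. Elsewhere the SAP writes out change from Baseline when it means change, for example for the co-primary variables in Section 2.5.1. In the correlation paragraph just above, in the same section, the bare names stand for the scores themselves. A programmer who follows that usage could enter the Week 16 value. The curve would then show how the level of SPI separates PASI responders, under a heading that promises responsiveness.

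If change is understood, its form still has to be inferred. The PASI criterion is a percentage, while Sections 2.5.2 and 3 work with absolute SPI change.

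At stake are the reported AUC, the unit of the odds ratio (per point of score, per point of change or per percent) and its direction. If nothing fixes the predictor, it could be picked after the data are seen.

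**Working it through.** The SAP gives no figure for this analysis, so there is none to reproduce. The check has three steps.

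**1. Do the candidate predictors differ?** Section 2.5.2 presents the severity scores in bands from 0 to 50. Four invented patients within that range, using the Section 2.1.1.3 formulas (difference = Week 16 − Baseline; percentage = 100 × difference / Baseline):

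| Baseline | Week 16 | Absolute change | Percentage change |
|---|---|---|---|
| 40 | 10 | −30 | 100 × (−30)/40 = −75% |
| 12 | 10 | −2 | 100 × (−2)/12 = −17% |
| 12 | 3 | −9 | 100 × (−9)/12 = −75% |
| 48 | 12 | −36 | 100 × (−36)/48 = −75% |

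The first two patients tie on score but not on change. The first, third and fourth tie on percentage change but not on points. The predictors rank patients differently, so the AUC can differ. The sign convention is a lesser matter. In a one-predictor logistic model, reversing the sign inverts the odds ratio but leaves the AUC of the fitted probabilities unchanged.

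**2. How much could the AUC move?** The documents cannot answer this, so all inputs here are assumed. Common inputs are: Baseline SPI (s) log-normal with median 18, capped at 50; remaining fraction of PASI distributed Beta(0.8, 3.2), which gives about 68% PASI 75 responders; PASI and SPI responses correlated 0.6 to 0.8; 200,000 patients per setting.

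- *Proportional SPI reduction:* remaining fraction Beta(0.8, 3.2), Baseline log-SD 0.3 to 0.7, measurement noise SD 0 to 4 points, 27 settings.
- *Additive SPI reduction:* mean 14, SD 7, floor at 0, Baseline log-SD 0.3 or 0.5, no noise, 6 settings.

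| AUC for PASI 75 | Week 16 score | Absolute change | Percentage change |
|---|---|---|---|
| Proportional | 0.65–0.87 | 0.58–0.74 | 0.65–0.89 |
| Additive | 0.66–0.79 | 0.74–0.87 | 0.71–0.84 |

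Under proportional reduction, percentage change beats absolute change by 0.06 to 0.25. It differs from the Week 16 score by only −0.01 to 0.07. Under additive reduction the order reverses: absolute change is best in all 6 settings, ahead of percentage change by at most about 0.05 and of the score by up to 0.12. Which predictor does best, and which ambiguity matters more, therefore follow from the assumed pattern of reduction. Neither is a property of this trial.

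**3. What does the text already settle?**
- *Visit.* The model sentence names none, but the aim it carries out says Week 16.
- *Score or change.* The heading speaks of change and the aim of corresponding reductions. A Week 16 score alone measures no reduction, so change is the natural reading.
- *Form of change.* Section 2.1.1.3 keeps the unqualified term for the simple difference and uses a separate term for the percentage. Sections 2.5.2 and 3 use the absolute form for SPI severity. Absolute change is the SAP's default, although the percentage PASI criterion keeps this from being conclusive.
- *Template.* In Section 5.4 the data set, response and predictor are all placeholders, because the code serves 2 indices × 4 PASI thresholds = 8 models. A blank predictor there is how a template is written.

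**The case for a change.** The strongest case for a change is that the SAP itself specifies this model and supplies code for it, so the predictor belongs here and is not a matter left to the protocol. The SAP is explicit about change elsewhere, so its silence here could be read as meaning the score. The objective in Section 1.2.3 is compatible with that reading and does not exclude it. Both forms of change are already derived under Section 2.5.2, so one sentence would close the gap at almost no cost.

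Much of this stands. The sentence is incomplete, the form of change has to be inferred, and a short clarification would be harmless. What does not stand is the step from an incomplete sentence to a faulty analysis. Nothing the SAP states leads to a wrong result. The score reading, if taken, still answers the stated objective of separating PASI responders from non-responders, and this ROC analysis is the only one in the SAP that serves it. The change reading answers the aim in Section 2.12. The possibility of choosing after seeing the data is real but carries little weight here, because no error rate is controlled on this analysis and no claim of efficacy rests on it. Asking for both forms would double 8 models to 16 without a demonstrated gain.

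**Conclusion.** No change is needed. This is a gap in wording that an analyst would fill sensibly from the same subsection: change from Baseline to Week 16, with the absolute form as the SAP's general convention. The time point is not missing.

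The choice of predictor can shift an exploratory AUC. The shift runs from near zero to about 0.25 in the assumed settings, and its direction depends on whether SPI falls in proportion to Baseline or by a fixed amount. Those figures rest entirely on assumed inputs and do not estimate anything in this trial. The paired tests on the co-primary endpoints, the PASI analyses and the safety summaries are untouched.

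The conclusion assumes that the report states which form of the score was modelled and in what unit, so that readers can interpret the odds ratio. That is ordinary reporting and needs no amendment.

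### In the exploratory Week 16 ROC analysis, untransformed DeLong 95% intervals under-cover if a PASI response class is small, and the SAP has no rule for that case

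*SAP*

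**What the plan says.** Section 1.2.3 lists as an exploratory objective "to evaluate the ability of SPI to discriminate between responders and non-responders based on PASI response". Section 2.12 (Responsiveness to change) carries it out at Week 16:

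- PASI response is dichotomised at 50%, 75%, 90% and 100% reduction. The text announces three criteria ("Three criteria of response will be examined to evaluate each score") but lists four.
- For each, "a logistic regression will be performed where proSPI (s) and saSPI (s) are the independent variables in separate models". Four thresholds and two scores give 4 × 2 = 8 curves.
- DeLong's methods "will be used to compute the AUC value and 95% CIs for each curve". Odds ratios with 95% intervals are also required, and "AUC values along with their 95% CIs will be presented".
- The data are restricted: "Exploratory analyses in this subsection will be on the FAS (observed data only").

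Section 5.4 supplies a plain PROC LOGISTIC call with a ROC statement. Neither section names a transformed or score-type interval, a minimum number of responders or non-responders, a penalised-likelihood option, or a rule for separation or an empty class.

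**The concern.** The precision of an AUC is limited by the smaller of the two classes. This is a single-arm study in which every patient receives active drug, and response for the ROC is fixed at one visit. The thresholds are nested, so PASI 50 has the fewest non-responders and PASI 100 the fewest responders. At either end one class could be small.

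The usual DeLong interval is the estimate plus or minus 1.96 standard errors. With a small class and an AUC near 1 it is too narrow, can run above 1, and shrinks to a point if the classes separate. The report would then print a nominal 95% interval that overstates how precisely SPI has been shown to discriminate PASI responders.

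**Working it through.** **Inputs from the SAP.** Section 3 concludes that "it can be estimated that a sample size of 100 evaluable patients would be sufficient", with 120 included. Section 2.12 gives the thresholds, scores, visit and interval method.

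**Inputs assumed.** The SAP gives no PASI response rate and no expected AUC. I therefore vary the smaller-class size m and the true AUC, using normal scores with equal variance in the two classes. SAP Sections 2.12 and 5.4 do not describe the interval as untransformed. That is the ordinary reading of a DeLong interval with no other form specified.

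**Step 1: the plan's own N.** For a paired difference at two-sided 2.5% with 90% power, n ≈ [SD × (2.2414 + 1.2816) / difference]².

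- proSPI (s): (14 × 3.523 / 5)² = 97.3, so 98; with the t distribution, 100.
- saSPI (s): (19 × 3.523 / 7)² = 91.4, so 92; with the t distribution, 94.

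The larger is 100, as stated, and 100 / (1 − 20/120) = 120. This confirms the N available to the ROC and says nothing about its precision.

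**Step 2: the DeLong interval.** With m patients in one class and n in the other, variance = S₁/m + S₂/n. S₁ and S₂ are the sample variances of each patient's proportion of correctly ordered pairs. The interval is AUC ± 1.96 √variance.

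- m = 0: no curve exists.
- m = 1: S₁ divides by m − 1 = 0 and does not exist.
- Complete separation: every proportion is 1, so S₁ = S₂ = 0 and the interval is [1, 1]. The maximum-likelihood odds ratio is then not finite.

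**Step 3: how small the class might be.** Assumed responder rates at N = 100, with m binomial and coverage averaged over trials where an interval exists:

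| Assumed response | Expected m | P(m ≤ 1) | Coverage, AUC 0.80 / 0.90 / 0.95 |
|---|---|---|---|
| 80% | 20 | 0.0% | 92.5 / 89.7 / 85.8% |
| 90% | 10 | 0.0% | 89.0 / 82.9 / 78.1% |
| 95% | 5 | 3.7% | 81.7 / 74.8 / 68.4% |
| 98% | 2 | 40% | 72.1 / 65.7 / 58.9% |

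**Step 4: coverage at fixed m.** There were 10,000 trials per cell (simulation error at most √(0.25/10,000) = 0.5 points). The AUC 0.85 column and the m = 25 row come from runs of 3,000 to 4,000 trials.

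| m | AUC 0.80 | 0.85 | 0.90 | 0.95 |
|---|---|---|---|---|
| 2 | 64.8% | – | 57.4% | 51.8% |
| 3 | 75.0% | 72% | 67.2% | 61.2% |
| 5 | 82.2% | 80-81% | 75.5% | 69.6% |
| 10 | 89.2% | 87% | 84.8% | 79.5% |
| 20 | 92.3% | – | 89.7% | 86.5% |
| 25 | – | 92-93% | 90-91% | 88% |
| 30 | 93.4% | – | 91.6% | 88.7% |
| 50 | 93.5% | – | 92.8% | 90.7% |

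Integer scores floored at 0, which produce ties, gave almost the same coverage at AUC 0.85 / 0.90 / 0.95: 70/68/61% with m = 3, 80/77/69% with 5, 87/84/79% with 10 and 93/91/89% with 25.

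**Step 5: the degenerate cases.** Zero-width intervals at AUC 0.80 / 0.90 / 0.95 occurred in 0.4 / 3.1 / 11.7% of trials with m = 3, in 0.01 / 0.7 / 3.9% with m = 5, and in 0 / 0.01 / 0.5% with m = 10. With m = 5 the upper limit exceeded 1 in 42 / 74 / 90% of trials.

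**Step 6: alternatives, same equal-variance settings.**

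- *Logit-transformed DeLong.* For m = 15 to 50 it covered 91.6-95.5%, against 83.3-93.5% for the plain interval. At m = 5 it covered 85-90%, and at m = 10 91-93%, among trials with AUC below 1. It is undefined at AUC = 1. Counting those trials as misses, it still does better: at AUC 0.95 and m = 3, 0.964 × (1 − 0.117) = 85%, against 61.2%.
- *Score-type (Newcombe).* The limits solve |estimate − A| = 1.96 √V(A). Here V(A) = A(1 − A)[1 + k(1 − A)/(2 − A) + kA/(1 + A)]/(mn), with k = N/2 − 1 = 49. Coverage was 94.3-96.7% for m = 2 to 10.

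Example: observed AUC 1, m = 5, n = 95. At A = 0.80 the bracket is 1 + 8.17 + 21.78 = 30.94, and 3.8416 × 0.80 × 30.94 / 475 = 0.200 = 1 − A. The score-type interval is about 0.80 to 1, where DeLong prints [1, 1].

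**The case against.** **The small class is assumed.** This stands. Nothing in the SAP says whether PASI 50 leaves 3 or 30 non-responders. A reader might infer that coverage is far below 95% at every threshold. The document does not support that: with 25 to 50 in the smaller class the shortfall is modest (88-94%), and only one or two thresholds may be affected.

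**Zero width is not the main failure.** This also stands. With 3 or more in the smaller class it reaches 4-12% only at AUC 0.95 with m of 3 to 5; at AUC 0.90 it is about 3% or less. An interval of [1, 1] would also be noticed.

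**Other measures of uncertainty exist.** A reader might take the AUC intervals to be the only ones for this objective. They are not: Section 2.12 also requires odds ratios with 95% intervals from the same models. Those fail too under separation, but not in general.

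**The score-type interval is not a guarantee.** Correct. With the non-responder SD two to three times the responder SD, it covered only about 82-95%, and was sometimes no better than DeLong with 10 to 25 non-responders. At a ratio of 2, AUC 0.85 and m = 25, both covered 90.7%; at a ratio of 3, 85.8% against 89.9%. Its advantage is at very small counts.

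**An earlier-visit ROC would have more even classes.** Perhaps, but the SAP does not show it, and Section 2.12 asks about Week 16. It would answer a different question and would not repair these intervals.

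**DeLong is a recognised method in an exploratory analysis.** True. That sets the priority; it does not restore coverage when a class is small.

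**Conclusion.** The point holds conditionally. The SAP fixes untransformed DeLong intervals for all eight curves and has no sparse-class rule. At N = 100 with equal-variance normal scores and true AUC 0.85 to 0.95, nominal 95% intervals cover about 61-72% with 3 patients in the smaller class, 70-81% with 5, 79-87% with 10 and 88-93% with 25. Under-coverage is the main effect. Separation, with [1, 1] and no finite odds ratio, is less frequent: about 12% of trials with 3 and 4% with 5 at AUC 0.95.

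The result rests on assumed class sizes, AUCs and score distributions, none of which the SAP states. No hypothesis or decision rule attaches to these AUCs, and the primary test, the key secondary analyses and the sample size are untouched. Priority is low.

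**What to change.** Amend Sections 2.12 and 5.4 before database lock:

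1. Keep the DeLong AUC estimate and, in general, report a logit-transformed DeLong 95% interval. It covered better than the plain interval in every equal-variance setting in Step 6.
2. When the smaller class has about 10 patients or fewer, or the observed AUC is 1, report a score-type (Newcombe) interval. Note that it is closer to nominal but not guaranteed if the spread of scores differs between classes.
3. Under separation, report Firth-penalised odds ratios with profile-likelihood intervals.
4. When a class has 0 or 1 patients, give the counts and no AUC interval.
5. Show responder and non-responder counts beside each AUC, and correct the number of criteria from three to four.

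Cost: a few lines of text and a short macro, with no new data. The downside is wider intervals.
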